10.0 Data and Specimen Banking

All data will be kept for 7 years after publication, as required by Northwestern University. Blood specimens will be banked in a freezer in the basement of [name] for future use. Specimens will not be stored linked to direct identifiers (only by randomly assigned participant identification number, as described below in data security section). The specimens will not be destroyed, and they will only be used in the future for research purposes. Specimens will be accessible by [name] and co-investigators with IRB approval.

11.0 Data and Specimen Management

11.1 Data Analysis Plan.

Phase 1. Stakeholders will contribute to intervention component development via interviews which will be digitally recorded; digital files will be stored on a password-secured network drive. Recordings will be transcribed verbatim and de-identified. Three coders will independently review the de-identified transcripts, identify emergent themes, and assign initial codes using constant comparative analysis. This iterative process codes data based on identified conceptual themes. Data will be organized using NVivo software. Coders will meet often to discuss and refine the emerging themes, and triangulate their perspectives. Once a final coding structure is identified, coders will independently return to the transcripts to re-examine them and recode as necessary to ensure consistency. Disagreements will be resolved through deliberation and consensus. Analysis will identify the three stakeholder groups (survivors, experts, community organizations) perspectives on desirable components for inclusion. All groups' perceptions of components, how to implement the proposed intervention and strategies for tailoring intervention content, and tactics for overcoming challenges to implementation will be integrated. These components will be vetted via the Breast Cancer Survivor Stakeholder Advisory Board Session. After vetting from the advisory board, the final 5 components will be selected for development.

Once components to be tested are identified and the app is under development, usability testing will begin. For this, survivors will be given a defined set of tasks to complete. They

PROTOCOL TITLE: Designing with Dissemination in Mind: Optimization of a mHealth Physical Activity Intervention for Breast Cancer Survivors (Fit2Thrive)

will be observed to determine the ease with which they navigate using various app functions (e.g. error rates, time to complete tasks, etc.). Survivors will also provide qualitative and quantitative feedback regarding features, ease of use, and likeability. Usability tests will be rapid and iterative. During the field testing period, design changes will be completed after receipt of 2 to 5 survivors' feedback and then tested with the next set of 2 to 5 survivors. The app will be refined to eliminate issues that impeded usability. We anticipate 10-20 survivors will be needed to achieve saturation on issues identified during testing. Following the field testing, they will participate in a session to provide feedback on the app features and functioning. Because consensus may be reached during the field testing before all participants have a chance to participate, survivors may or may not participate in the field testing and post-field testing sessions. Finally, survivors will participate in a final lab visit where they evaluate the close-to-final intervention and provide feedback.

Phase 2. The effects of the five individual intervention components will be examined by means of a factorial experiment (see Table 4 for an example). The final factors will be determined based on the findings from Phase 1 of the study. Although these components will be evidence-based and have been included in bundled PA interventions previously found to be successful, none of these prior studies were designed to estimate the impact of any individual component.

We chose a factorial experimental design factorial experiments have two characteristics essential to the success of MOST. These experiments: a) separate component effects enabling the estimation of the main effect contribution of each candidate component and interactions between components¹¹⁴ and b) are more economical compared to alternative designs because they often require substantially fewer subjects to achieve the same power and use less resources .^{114,115}

A complete factorial experiment requires $2^5=32$ experimental conditions. It is important to understand that this design should not be considered a multiple arm RCT. All of the estimated main effects and interactions will be based on all experimental conditions. Table 7 displays the experimental conditions for this study. For example, main effect of telephone support calls would be estimated by comparing the mean of experimental conditions 1-7 with the mean of conditions 8-16. Similarly, the main effect of the App+ would be estimated by comparing conditions 1-4 and 9-12 with conditions 5-8 and 13-16. Thus, all 256 participants will be included in all effect estimates.

Table 7. Experimental Conditions

Exp Condition	Support Calls	App+	Buddy	Online Gym	App Notifications
1	yes	no	no	no	no
2	yes	yes	no	no	no
3	yes	no	yes	no	no
4	yes	no	no	yes	no
5	yes	no	no	no	yes

PROTOCOL TITLE: Designing with Dissemination in Mind: Optimization of a mHealth Physical Activity Intervention for Breast Cancer Survivors (Fit2Thrive)

6	no	yes	no	no	no
7	no	yes	yes	no	no
8	no	yes	no	yes	no
9	no	yes	no	no	yes
10	no	no	yes	no	no
11	no	no	yes	yes	no
12	no	no	yes	no	yes
13	no	no	no	yes	no
14	no	no	no	yes	yes
15	no	no	no	no	yes
16	yes	yes	yes	no	no
17	yes	yes	no	yes	no
18	yes	yes	no	no	yes
19	yes	no	yes	yes	no
20	yes	no	yes	no	yes
21	yes	no	no	yes	yes
22	no	yes	yes	yes	no
23	no	yes	yes	yes	yes
24	yes	no	yes	yes	yes
25	no	no	yes	yes	yes
26	no	yes	no	yes	yes
27	yes	yes	yes	yes	no
28	yes	yes	yes	no	yes
29	yes	yes	no	yes	yes
30	no	no	no	no	no
31	no	yes	yes	no	yes
32	yes	yes	yes	yes	yes

Planned analyses for each aim are as follows:

Aim 1. All individual interviews will be digitally recorded; digital files will be stored on a password-secured network drive. Recordings will be transcribed verbatim and de-identified. Three coders will independently review the de-identified transcripts, identify emergent themes, and assign initial codes using constant comparative analysis. This iterative process codes data based on identified conceptual themes. Data will be organized using NVivo software. Coders will meet often to discuss and refine the emerging themes, and triangulate their perspectives. Once a final coding structure is identified, coders will independently return to the transcripts to re-examine them and recode as necessary to ensure consistency. Disagreements will be resolved through deliberation and consensus. Analysis will identify both aides' and clients' perceptions of implementing the proposed intervention, strategies for tailoring the existing intervention content, and tactics for overcoming identified challenges to implementation.

PROTOCOL TITLE: Designing with Dissemination in Mind: Optimization of a mHealth Physical Activity Intervention for Breast Cancer Survivors (Fit2Thrive)

All information obtained from direct observation will be entered and analyzed using descriptive statistics to determine the learnability, effectiveness, efficiency, errors, flexibility, memorability, and user satisfaction of the app components. We will also transcribe verbatim the de-identified digitally audio recorded files and use these data to further assess qualitatively any themes that emerge relative to the components' learnability, effectiveness, efficiency, errors, flexibility, memorability and user satisfaction. Finally, descriptive statistics (means, standard deviation, frequencies) of questionnaire-based feedback will be used to further assess the app's the learnability, effectiveness, efficiency, errors, flexibility, memorability and user satisfaction.

Data from participant interviews and questionnaires completed related to the field experiment will be analyzed as described, above, and used to refine the app until saturation is reached.

Aim 2. Feasibility and acceptability will be evaluated using the measures detailed above. The primary hypotheses are: a) 75% of eligible survivors will agree to participate in the intervention; (b) enrollees will demonstrate engagement by monitoring PA on >80% of the study days and using one or more additional app components at least weekly. Descriptive analyses (means, frequencies) will be used to describe these results. Data from post-intervention interviews will be digitally recorded; digital files will be stored on a password-secured network drive. Recordings will be transcribed verbatim and de-identified. Three coders will independently review the de-identified transcripts, identify emergent themes, and assign initial codes using constant comparative analysis. This iterative process codes data based on identified conceptual themes. Data will be organized using qualitative data analyses software. Coders will meet often to discuss and refine the emerging themes, and triangulate their perspectives. Once a final coding structure is identified, coders will independently return to the transcripts to re-examine them and recode as necessary to ensure consistency. Disagreements will be resolved through deliberation and consensus. Analysis will identify both aides' and clients' perceptions of implementing the proposed intervention, strategies for tailoring the existing intervention content, and tactics for overcoming identified challenges to implementation.

Aim 3 and Exploratory Aim 1. These aims are to determine the preliminary effectiveness of intervention components on minutes of accelerometer-measured moderate and vigorous PA (Aim 3) and PROs (physical function, fatigue, depression, QOL; Exploratory Aim). Our hypothesis is that a set of components will emerge as most effective for increasing PA and minimizing cost, but a second set of intervention component may emerge as having the largest, most cost-efficient impact on PROs. These hypotheses will be tested using intention-to-treat mixed linear model analyses to test differences in outcomes by intervention components. The study was not designed to have statistical power to detect differences over time with inferential tests. If descriptive statistics suggest that the intervention (a) is feasible and acceptable and (b) seems likely to increase PA, we will plan a future randomized controlled trial with sufficient power (>.80) to detect clinically-meaningful effects in this population. If we fail to achieve certain benchmarks for

PROTOCOL TITLE: Designing with Dissemination in Mind: Optimization of a mHealth Physical Activity Intervention for Breast Cancer Survivors (Fit2Thrive)

feasibility, acceptability, or safety, we will refine the protocol as needed prior to proceeding.

Exploratory Aim 2. This aim is to explore the relationship between the 5 intervention components and each BC progression (IL-6, IL-10, CRP and TNF α) and cardiometabolic (CRP, BG, TG, TC, HDL-C) biomarker. We will also examine effects on overall risk for each category using composite z-scores. Our hypothesis is a set of components will emerge as most effective for changing each biomarker, but a second set of components, which may not be the same, may emerge as having the greatest composite effect or being most cost-efficient to achieve these outcomes. We will employ an intention-to-treat (ITT) approach by including all participants recruited into the study regardless of compliance. These hypotheses will be tested using intention-to-treat linear mixed model analyses to test differences in outcomes by intervention components. We will also test 2-way interactions between selected intervention components. Because we will use effect (-1,1) coding rather than dummy (0,1) coding, the power for tests to detect main effects and interaction effects are identical for effects of identical size. These data will be used in conjunction with parent study data to determine which intervention components will be tested in a more definitive trial.

11.2 Power Analysis.

Because this is a pilot test to evaluate the feasibility, acceptability, and preliminary efficacy of the different intervention components, sample size planning was determined by resource constraints (vs. a power analysis) for the primary aims.

Dried Blood Spots. To determine if the sample size (n=256) is sufficient to address our

exploratory aim to explore biomarkers obtained via DBS, we conducted a power analysis to calculate the minimal detectable difference (MDD)¹¹⁶ for each biomarker assuming 20% attrition at 24 weeks, an alpha of 0.05, and two-sided testing. The MDD defines the difference that must exist between those with the component “on” vs. “off” to detect a statistically significant effect. We used standard deviations

Table 8. Minimal Detectable Differences

Marker	SD	ICC	Study	MDD
IL-6	1.1	0.80	Jones 2013	0.40 pg/mL
IL-10	3.8	0.80	Rogers 2012	1.37 pg/mL
TNF α	0.6	0.80	Jones 2013	0.21 pg/mL
CRP	2.4	0.44	Jones 2013	0.78 mg/dL
BG	7.8	0.49	Guinan 2013	2.57 mg/dL
HDL-C	0.3	0.87	Fairey 2005	0.11 mmol/L
TG	0.7	0.79	Fairey 2005	0.27 mmol/L
TC	0.3	0.75	Fairey 2005	0.10 mmol/L

from published BCS PA interventions¹¹⁷ and intra-class correlations (ICC) from [name] prior study,¹¹⁸ if available. Otherwise, a conservative ICC of 0.8 is assumed. Table 8 displays MDDs for component main effects and two-way interactions at 12 and 24 weeks. We have 80% power to detect differences at least equal to between group differences observed in prior intervention studies for all inflammatory^{119,120} and CVD markers^{121,122} except for BG. Given no study has evaluated specific PA intervention component effects on biomarkers in BCS in the context of a MOST design, we accept this limitation.

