Methodological Innovation: MOST to Design with D&I in mind from the Start. Intervention development typically consists of designing an intervention with multiple components and then testing whether the intervention, as a whole, has a significant effect in randomized clinical trials (RCT).⁸⁶ However, information about which intervention components contribute to the desired effect and which do not is necessary to continue to increase intervention effectiveness and efficiency. Because all intervention components are turned “On” in the treatment group and “Off” in the control group in a typical RCT, this information cannot be obtained. The Multiphase Optimization Strategy (MOST)^{25,87} is a comprehensive framework that supports optimizing an intervention by efficiently and systematically identifying the most promising intervention components and component levels. MOST is based on is based on the engineering principles of resource management and continuous optimization. The overall goal of MOST is to maximize public health impact (efficacy x intervention reach) using available resources. MOST is an emerging methodology that may be particularly useful for designing mHealth interventions with D&I in mind from the start because of its emphasis on optimization, an iterative design process and public health impact.^{20,88} Figure 3 describes how we plan to use MOST to design an optimized PA intervention for breast cancer survivors. MOST, like all theory-based approaches to intervention development, starts by using theory, scientific literature, clinical experience, and results from previous studies to establish a conceptual model (Step 1a). Based on prior work, we am proposing to use SCT for this study. We will complete steps 1b to 3b as part of the proposed project. Step 1b will involve further refinement of the model/component selection to inform Step 2, intervention/app design and usability testing. These steps will be performed in collaboration with relevant stakeholders (cancer survivors, clinicians, research experts). Step 3a will pilot test the feasibility, acceptability, and effects on PA and important patient reported outcomes (PROs) of each of the intervention components and component combinations. Step 3b involves collection of participant feedback and evaluation of the intervention components and combinations. The present study will provide the necessary preliminary data to apply for future grants steps 4a-5. The MOST framework has rarely been applied to the development of behavioral interventions, and to the best of our knowledge, has never been specifically applied to the development of a PA intervention in cancer survivors.

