7.3 Estimated date for study completion: June 30, 2020

8.0 Study Endpoints

8.1 Describe the primary and secondary study endpoints.

Primary study endpoint: intervention feasibility/acceptability.

Feasibility: This will be measured during the intervention, immediately post-intervention and after the follow-up period. Measures include:

- *Intervention reach:* # of participants enrolled/# of eligible individuals
- *Participant retention:* # of participants who drop out/# of participants randomized

PROTOCOL TITLE: Designing with Dissemination in Mind: Optimization of a mHealth Physical Activity Intervention for Breast Cancer Survivors (Fit2Thrive)

- *Intervention Adherence:* % of weeks adhered to exercise prescription during intervention period
- *Intervention Maintenance:* % of weeks adhered to exercise prescription during follow-up period
- *Intervention component engagement:*
 - During intervention: # of times, on average, participants interacted with each intervention component during intervention
 - During follow-up: # of times, on average, participants interacted with each intervention component during follow-up
 - Total: # of times, on average, participants interacted with each intervention component over intervention and follow-up

Acceptability: This will be measured via a process evaluation immediately post-intervention at 12 weeks and after the follow-up period at 24 weeks. This evaluation will assess the following:

- Perceived effectiveness of intervention components/app; use of app/intervention materials; plans to continue PA/app use; elements of intervention liked/disliked; satisfaction with program delivery, assessments and staff

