- *Intervention Adherence*: % of weeks adhered to exercise prescription during intervention period
- *Intervention Maintenance*: % of weeks adhered to exercise prescription during follow-up period
- *Intervention component engagement*:
 - During intervention: # of times, on average, participants interacted with each intervention component during intervention
 - During follow-up: # of times, on average, participants interacted with each intervention component during follow-up
 - Total: # of times, on average, participants interacted with each intervention component over intervention and follow-up

Acceptability: This will be measured via a process evaluation immediately post-intervention and after the follow-up period. This evaluation will assess the following:

- perceived effectiveness of intervention components/app; use of app/intervention materials; plans to continue PA/app use; elements of intervention liked/disliked; satisfaction with program delivery, assessments and staff

Screening

Physical Activity Readiness Questionnaire (PAR-Q)⁹⁶ This pre-screening questionnaire assesses cardiovascular disease history, symptoms, risk factors and other health issues. Women indicating ≥ 1 positive statements will be required to obtain medical clearance from their primary care physician or oncologist.

Other Measures

All measures will be used for both breast cancer survivor participants and buddies unless otherwise indicated. Assessment will be conducted at baseline, 3 weeks (survivors only), 12 weeks and 24 weeks.

Mobile Device Proficiency Questionnaire⁹⁸ This survey assess both assessing both basic and advanced proficiencies related to smartphone and tablet use across eight subscales: (a) Mobile Device Basics, (b) Communication, (c) Data and File Storage, (d) Internet, (e) Calendar, (f) Entertainment, (g) Privacy, and (h) Troubleshooting and Software Management.

Demographics. Data will be collected on participant's current age, race, ethnicity, employment status, number of children, education, marital status, income, height and weight.

Breast Cancer History. Participants will be asked to indicate their current menopausal status and provide details on the prior breast cancer diagnosis including: date of diagnosis, stage of disease, treatment type and duration and hormone receptor status. Women will be asked to indicate similar data for any cancer recurrences or second

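### No by-component comparison is specified for retention, adherence and maintenance, although Aim 2 asks about the feasibility of each component

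*Combined protocol and SAP*

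**What the plan says.** Section 8.1 declares "Primary study endpoint: intervention feasibility/acceptability". Three of its feasibility measures are defined on every randomised woman, with no split by component (8.1, repeated in 9.4):

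- retention, from the number "of participants who drop out/# of participants randomized";
- adherence, the percentage "of weeks adhered to exercise prescription during intervention period";
- maintenance, the percentage "of weeks adhered to exercise prescription during follow-up period".

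A fourth measure, engagement, is already component-specific: the number "of times, on average, participants interacted with each intervention component during intervention", with matching counts for follow-up and in total.

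The stated object is the components. Aim 2 in section 1.1 concerns candidate components. Section 2.3 gives this purpose for the third step of the framework: "pilot test the feasibility, acceptability, and effects on PA and important patient reported outcomes (PROs) of each of the intervention components and component combinations". Section 11.2 describes a pilot of the different components, sized by resources for its primary aims.

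The Aim 2 paragraph of section 11.1 says that feasibility and acceptability will be evaluated with the listed measures. It gives two hypotheses (75% uptake; activity monitored on more than 80% of days plus weekly use of another app component) and then says "Descriptive analyses (means, frequencies) will be used to describe these results". By-component mixed models are specified for physical activity and patient-reported outcomes (Aim 3, Exploratory Aim 1) and for biomarkers (Exploratory Aim 2). The progression statement under Aim 3 begins "If descriptive statistics suggest that the intervention (a) is feasible and acceptable", so it refers to a single intervention.

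**The concern.** No single intervention is delivered in Phase 2. Women are spread over 32 configurations, and the components for the next trial will be chosen from these data. If retention, adherence and maintenance are summarised only overall, the figures describe the average of that spread. A component that drives women out, or lowers adherence, cannot be identified from them. It could then be carried forward on its activity effect while overall feasibility looks satisfactory.

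No other section closes the gap. The missing-data check in 11.4 compares women with and without data on demographic and disease characteristics, not on assigned component. Section 13.1 carries the last observation forward for withdrawals who decline follow-up, so dropout that differs by component would also feed into the Aim 3 contrasts without any planned table to show it.

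**Working it through.** **1. The plan's design counts.** Section 11.1 gives 2^5 = 32 conditions and 256 women; sections 4.0 and 23.1 give about 128 women in the buddy condition. Coded as -1/+1, Table 7 has 32 distinct rows, each component is on in exactly 16, and all pairs of components are orthogonal. Hence 256/32 = 8 women per condition and 256/2 = 128 on versus 128 off for each component. The stated 128 buddies is reproduced.

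**2. What a pooled rate can show.** With equal allocation, pooled rate = (rate on + rate off)/2. A component that changes the rate by d moves the pooled rate by d/2 from its off value. The documents give no retention assumption for Aim 2, so this illustration borrows the 20% attrition at 24 weeks from the dried-blood-spot calculation in 11.2. The effect sizes are assumed.

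- No effect: 80% on, 80% off, pooled 80%.
- One component costs 14 points: (87% + 73%)/2 = 80%.
- Two components each cost 10 points, additively: pooled 80%, but women with both retain 80 - 2 x 10/2 = 70%.

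The pooled figure is the same in all three cases.

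**3. What the on/off contrast can show for retention, at 80%.**

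- 95% half-width, pooled: 1.96 x sqrt(0.80 x 0.20/256) = 4.9 points.
- 95% half-width, on minus off: 1.96 x sqrt(2 x 0.80 x 0.20/128) = 9.8 points (11.2 at 70% retention, 7.4 at 90%).
- Power at two-sided 0.05, normal approximation, 128 versus 128, centred on 80%: 52% for 10 points, about 80% for 14 points, 98% for 20 points.
- One condition of 8 women: 1.96 x sqrt(0.16/8) = about 28 points (rough at this size). Main effects are usable; condition-by-condition summaries are not.

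**4. Percentage of weeks adhered or maintained.** Detectable difference at 80% power = (1.960 + 0.842) x SD x sqrt(2/128) = 0.35 SD with complete data. No SD is given; over an assumed range of 20 to 40 points this is 7.0 to 14.0 points.

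**5. Predicting one package.** In the balanced design with an intercept and five main effects, the half-width at 80% retention is 1.96 x sqrt(6 x 0.16/256) = 12.0 points. With all two-way interactions (16 terms) it is 1.96 x sqrt(16 x 0.16/256) = 19.6 points.

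**6. Coding the contrasts.** The worked example in 11.1 compares conditions 1-7 with 8-16 for support calls. In Table 7, calls are on in conditions 1-5, 16-21, 24, 27-29 and 32. The example omits conditions 17-32 and puts conditions 6, 7 and 16 on the wrong side.

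**The case against.** The strongest reply is that much of the primary endpoint already works by component. Engagement is counted per component, acceptability covers perceived effectiveness of components, weekly surveys track use of the classes and the buddy, and up to 35 interviews are sampled by adherence and component assignment. This stands. A reader might infer that Aim 2 yields nothing about any component; the documents do not support that. What remains is that engagement with a component has no off comparison, and about 35 interviews cannot estimate an effect on dropout.

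Secondly, the sentence about descriptive analyses directly follows the uptake and engagement hypotheses, and means and frequencies could be tabulated by component. This also stands in part. A reader might infer that the plan rules out a by-component breakdown; it does not. It specifies none, and overall summaries are the natural reading.

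Thirdly, carrying forward the last observation for early withdrawals would pull a high-dropout component's activity result towards no change, and adherence overlaps with activity. That gives partial cover, but it neither shows nor quantifies the dropout.

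Finally, descriptive reporting suits a pilot sized by resources. Agreed: the request is for estimates with intervals, not for tests.

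**Conclusion.** The point holds for three measures: retention, percentage of weeks adhered and percentage of weeks maintained. The plan poses a component-level feasibility question, randomises so that it can be answered, and specifies no analysis that answers it for these measures. Reach precedes randomisation and cannot be split by component.

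The size is illustrative. A 14-point retention effect leaves the pooled figure unchanged at 80%, whereas the on/off contrast has about 80% power to show it; at 10 points the power is only 52%. These figures rest on 20% attrition borrowed from the biomarker calculation, an even 128/128 split, and assumed effects. No stated power figure is missed, because the plan gives none for Aim 2.

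A reader might go further and want a feasibility benchmark applied to the model-predicted package. The documents do not support that: section 11.1 mentions benchmarks without giving any for these three measures, and the prediction would carry about 12 points either way for a package chosen on the same data.

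**What to change.** In section 11.1, Aim 2, keep the overall descriptive figures and add the following:

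- For retention, percentage of weeks adhered and percentage of weeks maintained, report each component's on-minus-off main-effect difference with its 95% confidence interval, in all randomised women.
- Use the effect-coded factorial model already described for Exploratory Aim 2: risk difference or logistic for retention, linear for the percentages.
- Label these as estimates, not tests, and consider them alongside the activity effects when components are chosen for the next trial.
- If a predicted value for a package is reported, give it with its interval and as descriptive only.
- Code the contrasts from Table 7, and correct the worked examples in 11.1 to match it.

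The cost is a few sentences and a few models on data already collected, with no new participants or procedures. The downside is five extra contrasts per measure with wide intervals, about 10 points either way for retention at 80%.
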